7 DATA COLLECTION AND MANAGEMENT PROCEDURES

AIM 1: Only data from VA databases will be collected for participant identification and screening purposes. This data will be collected by the VA study data manager.

PROVIDERS:

For the semi-structured provider interviews, we will sample up to 20 VHA urologists from VHA facilities with the highest and lowest use of castration as primary treatment. We will use preliminary data from [name] CDA but then update the data using CDW Oncology data for the years 2016 and 2017 once our DART application is approved. We are also applying for access to Medicare claims data from VA Information Resource Center (VIReC) to validate we are not missing unidentified treatment with surgery or radiation therapy outside VHA. We plan to pull Medicare data on up to 20,000 patients. We will identify Urology Chiefs at each site using lists of providers from the most recent Federal Practitioner directory and national urologist email listserv. If possible, we will use CDW data to identify providers who meet the criteria of having experience caring for patients on ADT.

PATIENTS

We will use VA cancer registry data for years 2016 and 2017 to identify patients at high outlier sites on primary ADT for prostate cancer. Patients will be ineligible if they have dementia or other significant mental impairment noted in their medical record.

ACCESS TO DATA:

All identifiers, including interview recordings, will be stored in access restricted folders on VA servers behind the VA firewall. Only key study team members added to the AAVA IRB approved protocol personnel list will have access to data files containing PHI/PII. All personal identifiers will be stripped from the written verbatim transcripts of the interviews. Subjects will be instructed at the start of the interview to refrain from mentioning names of colleagues or from identifying the medical center.

DATA SAFETY MONITORING PLAN (DSMP):

[name] will be responsible for reporting all adverse events that might arise during the course of the study to the University of Michigan and the Ann Arbor Veterans Affairs Health System IRB. Adverse Events during this study would likely consist only of breaches in confidentiality. The following precautions have been taken to prevent this. However, should such breaches occur, [name] will report these occurrences to the overseeing IRBs within 48 hours.

All identifiers, including interview recordings, will be stored in access restricted folders on VA servers

behind the VA firewall. Only key study team members added to the AAVA IRB approved protocol personnel list will have access to data files containing PHI/PII. All personal identifiers will be stripped from the written verbatim transcripts of the interviews. Subjects will be instructed at the start of the interview to refrain from mentioning names of colleagues or from identifying the medical center. All research data will be de-identified at the termination of the study, if not sooner. Study data will be moved to the VA CCMR data repository and destroyed by the CCMR data manager six (6) years following the end of the Fiscal Year after completion of the research project as described in the VA Records Control Schedule.

AIMS 2: The survey/DCE will be pilot tested at study consultants' sites and refined based on feedback and any necessary troubleshooting. Once the survey/DCE is finalized, it will be disseminated to providers on the Society of Government Service Urologists (SGSU) listserv. Study staff will send email invites to up to 500 providers. The email invite will include an attached study information sheet and a link to the survey/DCE. Email invites will be sent from [name] VA email account. We will send up to 3 email invites to the listserv (allowing at least one-two weeks between each invite) and collect up to 400 completed surveys/DCEs. The survey/DCE will be hosted on the Sawtooth Software platform and **all data will be collected anonymously**. Providers completing surveys/DCEs will receive a \$50 Amazon eGift Card.

AIM 3: The pilot will be conducted at 4 VA sites under the oversight of the VA Ann Arbor RDC/IRB.

AIM 4:

We plan to retrospectively analyze data from VA facilities across the United States to determine what facility level factors are associated with low value ADT use in clinically localized prostate cancer. Data will be collected from national VA CDW, workforce (VSSC), and Central Cancer Registry data by the study data manager. All identifiers will be stored in access restricted folders on VA servers behind the VA firewall. Only key study team members added to the AAVA IRB approved protocol personnel list will have access to data files containing PHI/PII. Study data will be moved to the VA CCMR data repository and destroyed by the CCMR data manager six (6) years following the end of the Fiscal Year after completion of the research project as described in the VA Records Control Schedule.

8 DATA ANALYSIS

AIM 1:

Interview data will be transcribed, coded and entered into NVivo software for analysis. We will use a preliminary coding scheme based on the Theoretical Domains Framework (TDF) and prior work by Huijg and Birken consisting of a three step process including: 1) coding affirmative and negative utterances regarding ADT use as localized treatment into TDF domains, 2) collecting responses across respondents into themes, 3) tallying the total number of mentions per theme, as well as conflicting beliefs within a theme (e.g., ADT is good vs. ADT is bad), according to the TDF domains, with particular emphasis on those included in our conceptual model. This qualitative work will inform Aim 2 and gather rich information for our proposed pilot intervention strategies.

AIMS 2:

Discrete choice experiments are based on Random Utility Theory which assumes participants will select responses with the most personal utility.^{80,83} Because respondents respond to a variety of choice sets, we will be able to estimate the relative priority of our barrier attributes and their levels. We will model urologists stated preferences providing quantitative information about the relative value, or utility, providers place on barrier attributes such as *physician autonomy* or *clinical time*, for example, using the equations below. There are ~250 urologists on the listserv. If 50% respond: 125 surveys with ~5 scenarios – 625 scenarios x 5 attributes = 3125 data elements for analysis. [name] is an expert in multi-level and multinomial regression techniques and will conduct the analyses with direction from Drs. [name] and [name] given their DCE expertise. Our methods will adjust for dependency of responses within individuals as they respond to different choice sets and will be modeled after published DCEs according to the following example equation:

Utility = (Constant) + β_1 (e.g., physician autonomy) + β_2 (e.g., clinical time) ...

We will assess for model fit and need for random parameters among the attributes. Attribute levels will range from -1 for our reference level to +1 for the alternative to allow determination of relative importance.⁸⁰ Our outcomes will be based on the beta parameter values (β_1 , β_2 , etc.) and standard errors that correspond to each attribute where a negative value will indicate preference for the reference group, statistical significance will be set at 0.05. Once we have our leading barrier attributes and corresponding TDF domains, we will select the most relevant candidate evidence-based behavior change technique components based on prior work by Michie et al.⁴⁷ to guide tailoring of pilot de-implementation interventions. We also plan to adjust our models for facility-level ADT rates, and perform a subgroup analysis for facilities with high primary ADT rates to better understand barriers to tailor towards

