5 SUBJECT ENROLLMENT

No subject enrollment will take place at UM.

VA PROVIDERS:

We will purposefully sample up to 20 urologists from high outlier facilities with highest and lowest use of chemical castration with androgen deprivation therapy (ADT) as primary treatment. Facilities will be updated using our algorithm combined with Medicare claims data for years 2016 and 2017 obtained from the VA Information Resource Center (VIReC) to validate we are not missing unidentified prostate cancer treatment outside VA.

Provider data from facilities with the highest and lowest rates of chemical castration for localized disease will be collected using lists of providers from the most recent Federal Practitioner directory and national urologist email listserv. We will identify Urology Chiefs at each site using lists of providers from the most recent Federal Practitioner directory and national urologist email listserv. [name] will email Urology Chiefs, describe participation in the study, and request approval to contact facility urologists for interviews.

Urologists will be emailed a study information sheet (to be submitted with a future amendment prior to start of recruitment activities) briefly describing the nature and purpose of the study as well as the types of questions they will be asked. The option to refuse participation will be clearly stated. Urologists who respond to emails agreeing to participate will be contacted either by phone or email and screened for purposeful sampling (e.g., do they routinely prescribe ADT). Any urologist who has experience caring for prostate cancer patients on ADT and expresses interest in prostate cancer care will be eligible to participate. Providers who are eligible and agree to be interviewed will be contacted by phone or email and scheduled for an interview. If email responses are below our target recruitment number, we may follow up recruitment emails to providers with 1 or 2 phone calls. We will also consider interviewing non-physician providers (e.g., nurse practitioners) if they prescribe a significant amount of ADT.

VA PATIENTS:

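### Does the 3125 count overstate the size of the discrete choice experiment, and does its list of about 250 clash with the ceilings of 500 invitations and 400 completes?

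*Combined protocol and SAP*

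**What the plan says.** Section 8, under Aim 2, rests the experiment on random utility theory, which "assumes participants will select responses with the most personal utility". The outcome is modelled by an example equation with a constant and one coefficient per attribute. The size statement begins "There are ~250 urologists on the listserv", assumes that half respond, and runs through 125 surveys and about five scenarios each to "625 scenarios x 5 attributes = 3125 data elements for analysis". It gives no power, target effect or confidence-interval width. The same paragraph says "Our methods will adjust for dependency of responses within individuals". The next adds that the need for random parameters will be assessed and that coefficients will be read with their standard errors at the 0.05 level.

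Section 7, under Aim 2, describes the fieldwork. The survey is to be "disseminated to providers on the Society of Government Service Urologists (SGSU) listserv". It continues "Study staff will send email invites to up to 500 providers", allows up to three mailings, and plans to "collect up to 400 completed surveys/DCEs".

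A differently described list appears in Section 5 and in the Aim 1 part of Section 7. There, urology chiefs and other providers for interview are found through the "most recent Federal Practitioner directory and national urologist email listserv".

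Section 3 says that Aims 2 and 3 have not yet been developed. Section 9 leaves quality control for both aims to be determined.

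**The concern.** Two things catch the eye.

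The first is the unit. In a random-utility model each scenario ordinarily yields one choice, and the attributes stand on the right-hand side of the equation. Multiplying scenarios by attributes counts predictor values. Every coefficient is estimated from the same 625 or so choices, which are themselves grouped within 125 people. A reader who took 3125 as the sample size would think the experiment far more precise than it can be. The coefficients are to decide which barriers the Aim 3 pilot strategies address, so overstated precision could lead to a poorly supported ranking of barriers.

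The second is the sampling frame. Section 8 counts about 250 urologists on a list it does not name at that point. Section 7 names the list and sets ceilings of 500 invited providers and 400 completes. If the two sections mean the same list, both ceilings exceed its membership. If they mean different lists, the expected number of completes could differ from 125.

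**Working it through.** **Inputs.** From Section 8: about 250 on the list, 50% response, about 5 scenarios per survey, 5 attributes. From Section 7: at most 500 providers invited, at most 400 completes.

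**The plan's own figure.**
- 250 × 0.50 = 125 surveys
- 125 × 5 = 625 scenarios
- 625 × 5 = 3125

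All three reproduce exactly.

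**What a misuse of 3125 would cost.** 3125 / 625 = 5, and √5 = 2.24. Entering 3125 as n in a precision formula would make standard errors 2.24 times too small, before any clustering.

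As an illustration, assume two alternatives per scenario, −1/+1 coding, coefficients near zero and levels that always differ between the alternatives. The information per choice is then 1.
- From 625 independent choices: SE = 1/√625 = 0.040.
- From 3125 treated as independent: SE = 1/√3125 = 0.018.
- With an assumed within-person correlation of 0.3 and 5 choices each: design effect = 1 + 4 × 0.3 = 2.2; effective choices = 625 / 2.2 = 284; SE = 1/√284 = 0.059.

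The documents give neither the number of alternatives nor a correlation, so these values only show scale.

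**Does the plan make that misuse?** No. Nothing is computed from 3125. The standard errors come from the fitted model, which is to account for dependence within respondents. They will reflect the choices actually made, whatever count was printed beforehand.

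**The list, read two ways.**

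| Reading | List size | Expected completes at 50% | Expected choices | 500 invitations as share of list | 400 completes as share of list |
|---|---|---|---|---|---|
| Sections 7 and 8 mean the same list | 250 | 125 | 625 | 500/250 = 200% | 400/250 = 160% |
| The list holds 500 (assumed; stated nowhere) | 500 | 250 | 1,250 | 500/500 = 100% | 400/500 = 80% |

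In the first row neither ceiling can be reached. In the second the invitation limit equals the list, and expected completes (250) stay below 400. So on both readings, at the plan's own response rate, neither ceiling cuts the sample short.

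If the list is the larger one, Section 8 understates the expected size by a factor of 250/125 = 2. By the same square-root rule its implied standard errors are then √2 = 1.41 times too large, which errs on the cautious side.

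**The case for a change.** The strongest case for a change is that printed numbers should be right and should agree. A later precision statement, particularly one for the planned subgroup of facilities with high ADT rates, would naturally start from the Section 8 figures, and someone might start from the wrong one. The limit of 500 counts providers, and the number of mailings is capped separately at three, so repeat invitations do not explain why it exceeds 250. Section 7 also shortens the named society list to *the listserv*, the term Section 8 uses, so the natural reading is one list whose membership is below both ceilings.

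Part of this stands. The two sections are not reconciled, and 3125 tells the reader nothing about precision beyond the 625 and 125 printed just before it.

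The rest does not carry. The plan calls 3125 a count of data elements, not a sample size or a number of independent observations, and as a count of attribute values it is literally correct. It is not the only size information either, since Section 7 gives the two ceilings. The society list is the only one named for this survey. The national urologist list appears only in identifying Aim 1 interviewees and chiefs, so analysts need no extra statement to tell them apart. A ceiling above the list size is simply never reached.

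**Conclusion.** No change to the plan is needed. The fivefold ratio of 3125 to 625 is real as arithmetic, but it enters no calculation. The 2.24-fold understatement of standard errors is hypothetical and is not a property of this plan. The mismatch between about 250 on the list and limits of 500 and 400 is a loose end in the wording. If the plan is followed as written, the survey goes to the named list, choices are collected up to limits not expected to bind, and a model allowing for clustering is fitted, with the same results whether or not the text is tidied.

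This rests on three assumptions: that each scenario yields one choice, which is the ordinary format though not stated; that the within-person adjustment is carried out as Section 8 promises; and that response is near the plan's 50%. It does not show that 625 choices are enough. The documents set no target against which to judge that, and Section 3 describes Aim 2 as still undeveloped. Any later precision statement should start from the choices and the respondents, as an analyst fitting this model would do in any case.

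### Adjusting the Aim 2 choice models for facility ADT rate cannot show how barrier weights differ at high-rate facilities; attribute-by-rate interactions should be prespecified

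*Combined protocol and SAP*

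**What the plan says.** All of this is in section 8, Data Analysis, under Aim 2, unless noted.

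- **Theory:** "Discrete choice experiments are based on Random Utility Theory which assumes participants will select responses with the most personal utility".
- **Model:** the example equation is "Utility = (Constant) + β_1 (e.g., physician autonomy) + β_2 (e.g., clinical time" and so on. It contains no facility term. The role of the constant is not defined, and the text does not say whether respondents must choose or may opt out.
- **Methods:** the analyst "is an expert in multi-level and multinomial regression techniques and will conduct the analyses". The plan also says "We will assess for model fit and need for random parameters among the attributes".
- **Coding and outcomes:** "Attribute levels will range from -1 for our reference level to +1 for the alternative to allow determination of relative importance". The outcomes are the attribute coefficients and their standard errors, and "statistical significance will be set at 0.05".
- **Facility rate:** "We also plan to adjust our models for facility-level ADT rates, and perform a subgroup analysis for facilities with high primary ADT rates". The reason given is to understand which barriers tailoring should address. How the rate enters the model is not stated. No cutoff or expected size is given for the high-rate group, and no comparison with the other facilities is described.
- **Sample:** "There are ~250 urologists on the listserv", with 125 surveys expected. Section 7 instead allows up to 500 invitations and up to 400 completed surveys.
- **Anonymity:** sections 7 and 11.2 say the survey data are collected anonymously. No facility question is described.

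**The concern.** In a random utility model the respondent's choice depends only on differences in utility between the options shown. Anything that is constant across those options drops out of the difference. A facility's ADT rate is constant in this sense, so adding it in the usual way does not let attribute weights depend on it. A report could then say that the models controlled for facility use while giving the same, or nearly the same, coefficients.

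Aim 2 feeds the tailoring of the Aim 3 interventions, so whether high-rate facilities weigh barriers differently is a practical question. As written, it rests on a subgroup fit alone. That fit uses only part of the data and has no planned comparison with the rest.

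**Working it through.** **1. The plan's own count.** 250 × 0.50 = 125 respondents; 125 × 5 = 625 scenarios; 625 × 5 = 3125 data elements. This reproduces exactly. The plan gives no power, effect size or subgroup size.

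**2. Rate as a covariate, forced choice.** For respondent i with facility rate z, and options j and k:

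U_ij − U_ik = β′(x_ij − x_ik) + γ(z_i − z_i) = β′(x_ij − x_ik).

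γ is not identified and β is unchanged. Check on simulated data (125 respondents, 5 pairs, 5 attributes coded −1/+1): the log-likelihood is −403.1736 with and without z, all five coefficients agree to 4 decimals, and the information on γ is 3.5e-30.

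**3. Rate through the constant, with an opt-out.** The term is now estimable: coefficient 0.46, likelihood ratio 27.1 on 1 df in one simulated example. It measures willingness to accept any option, not the weight of a particular barrier. In 200 simulated datasets where weights truly varied with rate, adding it moved the most affected attribute coefficient by 0.01 on average (maximum 0.035), against a full-sample standard error of about 0.065. In a format where one profile is accepted or refused, with a strong assumed rate effect on the constant (0.8 per SD), the mean shift was about 0.04.

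**4. Attribute-by-rate interactions.** These do not cancel, because z multiplies (x_ij − x_ik). In the forced-choice example they are estimable (likelihood ratio 22.2 on 5 df).

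**5. Precision for the quantity of interest, the weight at a high-rate facility.** Assumptions: top quarter is high-rate (31 respondents, 31 × 5 = 155 choices), rate normal and standardised, linear rate effect, random attribute levels (information 0.5 per choice when coefficients are near 0), no within-person correlation.

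- Full-sample SE, main effect or slope per SD: 1/√(625 × 0.5) = 0.057.
- Mean rate in the top quarter: about 1.27 SD.
- SE of the predicted weight there: 0.057 × √(1 + 1.27²) = 0.057 × 1.616 = 0.092.
- SE from the subgroup fit: 1/√(155 × 0.5) = 0.114.
- Ratio: 0.092 / 0.114 = 0.81, so about 20% lower.

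Simulation with non-zero coefficients gives larger values in nearly the same ratio: about 0.11 against 0.14 (0.11 / 0.14 = 0.79).

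**6. Power to detect that a weight changes with rate** (simulated, 125 respondents, two-sided 0.05):

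| True change per SD | Continuous interaction | Top quarter versus rest |
|---|---|---|
| 0.10 | 34% | 21% |
| 0.15 | 65% | 33% |
| 0.20 | 90% | 61% |
| 0.30 | 100% | 90% |

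A second simulation at 0.20 gave about 87% against 59%.

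**7. Sensitivity.** At 400 completes the SEs shrink by √(125/400) = 0.56, to about 0.06 and 0.08, in the same direction. At 125 respondents, high-rate shares of 10%, 25% and 50% give 12, 31 and 62 respondents, with subgroup SEs (random levels) of 0.183, 0.114 and 0.080.

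**The case against.** The strongest reply is that the plan does not commit to the form that fails. The equation is offered as an example, it has a constant, the choice format is open, and random parameters are to be considered. To adjust could be meant to include interactions. A reader might infer that the adjustment does nothing at all. The documents do not support that: if an opt-out is offered, the rate can enter through the constant and be estimated. What stands against the plan is that no wording in it lets attribute weights depend on the rate. Random parameters allow weights to vary between respondents but do not tie that variation to facility rate.

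A reader might also infer that the subgroup is small and too imprecise to use. The documents give neither its size nor a precision target, and section 7 allows far more than 125 completes. Nor is it fair to set a subgroup coefficient's SE beside that of an interaction slope, since they measure different things. On the matched comparison above the gain in SE is about 20%, not half.

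Finally, the overall attribute coefficients, which are the main Aim 2 output, are essentially unaffected, and this analysis informs a pilot. That also stands, and it limits the weight of the point.

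**Conclusion.** The point holds as a cheap and worthwhile improvement, not as an error that invalidates Aim 2. On its ordinary reading the planned adjustment cancels (forced choice) or mainly moves the constant (opt-out). In neither case does it answer the stated question about high-rate facilities. The cancellation is algebra and rests on no assumed figures.

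The size of the gain does rest on assumptions: 125 respondents, five pairs, top quarter as high-rate, a linear rate effect and no within-person correlation. Under these, the SE of a weight at a high-rate facility is about 0.11 against 0.14, and power for 0.20 per SD is about 87–90% against about 60%. These figures are illustrative.

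A separate condition applies to every version. Unless the anonymous survey records the facility's rate or rate band, neither the adjustment, the subgroup nor the interaction model can be run.

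**What to change.** In section 8, Aim 2:

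1. Replace the adjustment with attribute-by-facility-rate interactions, with the rate centred, in one model on all respondents. If an opt-out is offered, add rate-by-constant as well.
2. Report attribute weights with confidence intervals at a named high-rate and a named low-rate facility level, and test the interactions.
3. Keep the high-rate subgroup fit as a sensitivity check, with its cutoff stated in advance. It checks the linearity assumption.
4. State whether the choice is forced or includes an opt-out.
5. Add a survey item for facility rate, or a rate band coarse enough to preserve anonymity.
6. Reconcile the ~250 listserv members and 125 surveys in section 8 with the 500 invitations and 400 completes in section 7.

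The analysis change costs some wording, up to five more coefficients (six with rate-by-constant) and an assumed linear rate effect. The survey item must be in place before the survey is sent out.
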